Appendix E: Special studies specimen collection and shipping report

1. OBJECTIVES

1.1 Study Design

The goal of this randomized, placebo controlled, phase II/III trial is to evaluate isoquercetin as a novel anticoagulant in patients with advanced cancer (pancreatic, non-small cell lung cancer, and colorectal cancer). The primary goal of the phase II study is to assess the relative reduction in D-dimer levels following isoquercetin administration and evaluate safety. Based on efficacy and safety data, a dose of isoquercetin will be selected for continued enrollment into a phase III trial in order to evaluate the effectiveness of isoquercetin in preventing VTE in cancer patients.

1.2 Primary Objectives

- The phase II primary objective is to evaluate the efficacy of isoquercetin to reduce Ddimer values
- The phase III primary objective is to assess the effectiveness of oral isoquercetin to prevent venous thromboembolic events in cancer patients

1.3 Secondary Objectives

- To investigate the cumulative incidence of VTE according to tissue factor bearing microparticle status (and isoquercetin randomization). To evaluate the cumulative incidence of major hemorrhage between the groups of patients treated with isoquercetin versus placebo.
- To assess overall survival according to randomization and tissue factor bearing microparticle status
- To investigate the cumulative incidence of total or symptomatic VTE in all treatment arms (and according to tissue factor bearing microparticle status)
- To study the influence of isoquercetin on TFMP levels and change in TFMP levels over time.
- To evaluate the cumulative incidence of VTE in patients with elevated TFMP as well as very elevated d-dimer (>1500 mcg/L) overall and according to randomization.
- To assess for correlation between complete blood count, ECOG, histology, stage, Ddimer, and levels of tissue factor bearing microparticles
- To investigate the influence of chemotherapy, blood counts, growth factors, ECOG performance status on tissue factor bearing microparticle levels as well as VTE risk.
- Influence of VTE and isoquercetin on Quality of Life (QOL)
- To investigate the association between isoquercetin plasma concentrations, inhibition of protein disulfide isomerase activity, and reduction in D-dimer.
- To evaluate the efficacy of isoquercetin to reduce D-dimer or VTE in cancer patients based on levels of circulating tissue factor bearing microparticles or Khorana risk model
- To compare VTE rates at completion of phase II with historical rates of VTE in similar population

CONFIDENTIAL

This document is confidential. Do not disclose or use except as authorized.

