2.2 Study Disease and correlative studies background

The prothrombotic state associated with malignant disease has been a recognized entity since the 1800's. Almost 1 in 5 cases of venous thromboembolism (VTE) are thought to be related to cancer, and thrombosis is the second leading cause of mortality in cancer populations.³⁵ The risk of thrombosis attributed to the malignant state is not uniform across all histological diagnoses. There is a 10-fold greater rate of VTE among patients suffering from ovarian, brain, and pancreatic cancers compared to those with other histologies.³⁶ Randomized clinical trials have demonstrated a small absolute risk reduction in VTE with primary thromboprophylaxis of low molecular weight heparins. The absolute risk of VTE in these unselected cohorts is low (3-5%) and thus the benefit of daily injection and potential risk for bleeding has tempered enthusiasm for non-targeted thromboprophylaxis approaches. Different models and biomarkers are under investigation to identify those patients who are highest risk of developing thrombosis and thus would benefit the most from primary thromboprophylaxis. Khorana and colleagues developed and validated a scoring model that identified higher risk patients based on elevated platelet count, white blood cell count, body-mass index, and anemia.³⁷

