3.1 Eligibility Criteria

Participants must meet the following criteria on screening examination to be eligible to participate in phase 2 and 3 of the study:

3.1.1 Participants must have histologically confirmed malignancy that is metastatic or currently unresectable.

Eligible malignancies include:

- Adenocarcinoma of the pancreas (currently unresectable or metastatic)
- Colorectal (stage IV)
- Non-small cell lung cancer (currently unresectable stage III or stage IV)
- 3.1.2 Receiving or scheduled to receive first or second line chemotherapy (within 30 days of registration)
- 3.1.3 Minimum age 18 years. Because limited dosing or adverse event data are currently available on the use of isoquercetin in participants <18 years of age, children are excluded from this study but will be eligible for future pediatric isoquercetin trials.
- 3.1.4 Life expectancy of greater than 4 months.
- 3.1.5 ECOG performance status ≤ 2 (see Appendix B).
- 3.1.6 Patient must be able to swallow capsules (phase III only)
- 3.1.7 Participants must have preserved organ and marrow function as defined below:

Absolute neutrophil count \geq 1,000/mcL

CONFIDENTIAL This document is confidential. Do not disclose or use except as authorized. $\begin{array}{l} \mbox{Platelets} \geq 90,000/mcL\\ \mbox{PT and } \mbox{PTT} \leq 1.5 \ x \ institutional \ upper \ limit \ of \ normal\\ \mbox{Total bilirubin} < 2.0 \ mg/dl\\ \mbox{AST (SGOT)/ALT (SGPT)} \leq 2.5 \ X \ institutional \ upper \ limit \ of \ normal\\ \mbox{Creatinine} < 2.0 \ mg/dl \end{array}$

- 3.1.8 The effects of isoquercetin on the developing human fetus are unknown. For this reason, women of child-bearing potential and men must agree to use adequate contraception (hormonal or barrier method of birth control; abstinence) prior to study entry and for the duration of study participation. Should a woman become pregnant or suspect she is pregnant while participating in this study, she should inform her treating physician immediately.
- 3.1.9 Ability to understand and the willingness to sign a written informed consent document.

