- 14.1.2 The primary aim of the **phase III trial** is determine whether isoquercetin reduces the cumulative incidence of symptomatic or proximal VTE in cancer patients at 56 days.
 - 14.1.2.1 **Study design:** The trial is a randomized, placebo-controlled, doubleblinded phase III trial. Study subjects are randomized to placebo or isoquercetin. The structure of the study matches the phase II study, the central differences being that VTE is the primary endpoint and a single isoquercetin arm is compared to placebo.
 - 14.1.2.2 **Randomization:** Central randomization (1:1) will be performed by QACT Office at DF/HCC and stratified by cancer diagnosis and institutions.
 - 14.1.2.3 Accrual: Anticipated accrual is 20 patients per month across all sites.

14.1.2.4 Sample size justification:

The overall incidence of thrombosis in cancer populations varies between 2-40% based on histology, stage, chemotherapeutics, additional risk factors and mode of surveillance (imaging or symptomatic events). The overall cumulative incidence of VTE in recently conducted MicroTEC study with similar eligibility criteria and study design was 11.3%. The estimate of isoquercetin benefit is based on data from primary thromboprophylaxis trials that typically achieve VTE rates of 4% or less.^{60,61} Based on the estimated VTE rates of 11% in the placebo and 4% isoquercetin arms, a total of 281 isoquercetin-treated subjects and 281 placebo-treated subjects would be required to reject the null hypothesis that the failure rates for experimental and control subjects are equal with probability (power) 0.85. The 1-sided type I error probability associated with this test of this null hypothesis is 0.025. In order to adjust for death or dropout of 5% prior to 56 days, the sample size is increased by an additional 28 patients. We plan an interim analysis for efficacy or futility after 50% of patients have been randomized that will be guided by O'Brien-Fleming boundaries. This will require an additional increase in sample size of 5% or 28 patients. Therefore, we plan to enroll a total of 618 patients. A total of 30 patients enrolled in the phase II trial will be included in the total accrual target and final VTE endpoint analysis.

14.1.3 Primary endpoint analysis will be performed on an intention to treat basis following randomization for all patients who undergo baseline assessment for the presence of VTE and at least one dose of study medication. The cumulative incidence of VTE

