14.2 Secondary endpoint analysis

- Cumulative incidence of VTE in cancer patients with or without tissue factor bearing microparticles will be assessed for isoquercetin or placebo arms by a competing risk analysis and differences evaluated by the Gray test. We previously identified elevated tissue factor bearing microparticles as a significant risk factor for developing thrombosis with a cumulative incidence of 27-38%.⁴⁵ We also will evaluate whether isoquercetin reduces the cumulative incidence of symptomatic or proximal VTE in cancer patients with elevated tissue factor bearing microparticles. Based on our previous data, we anticipate that approximately 45% of patients enrolled will have elevated tissue factor bearing microparticles (N=278) and half will be randomized to placebo or isoquercetin. Based on estimated VTE rates of 20% in the placebo and 7% in the isoquercetin arms for individuals with high tissue factor bearing microparticles, the probability (power) to reject the null hypothesis is 0.84. The 1-sided type I error probability associated with this test of the null hypothesis is 0.025 (Fisher exact test).
- The cumulative incidence of major hemorrhage between the groups of patients treated with isoquercetin versus those without. Analysis will include time to first major bleed, overall incidence of bleeding and analysis of bleeding events over time.
- Overall survival according to randomization and tissue factor bearing microparticle status will be analyzed by Kaplan Meier and significance testing by log-rank analysis
- Cumulative incidence of total or symptomatic VTE at 2 months in all treatment arms (and according to tissue factor bearing microparticle status)
- Influence of isoquercetin on TFMP levels and change in TFMP levels over time. This will be analyzed by continuous measurement of difference using ANOVA approach.
- Cumulative incidence of VTE in patients with elevated TFMP and very elevated ddimer (>1500 mcg/L) overall and according to randomization.
- Correlation between complete blood count, d-dimer, ECOG, histology, stage, and TFMP levels will be determined by assessing the correlation coefficient by standard methods (Pearson or Spearman's coefficients).
- Linear regression modelling will be performed to assess the influence of chemotherapy, blood counts, growth factors, ECOG performance status on TFMP levels.

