- Fine and Graey regression modelling will be performed to assess the influence of chemotherapy, blood counts, growth factors, ECOG performance status on VTE risk.
- Quality of Life (QOL) will be assesses using EORTC QLQ-30 version 3 which is an internationally validated and widely utilized questionnaire.⁵⁷ Scoring is based on responses to 30 questions dealing with functional quality and symptom burden. The questionnaire will be completed at baseline visit and end of treatment assessments. All are reported on a range 0-100; a high score represents a high level of functioning and QOL. We will analyze the data using analysis of variance techniques if the QoL has constant variance across groups (based on VTE rates and treatment groups). If not, we will use the Kruskal-Wallis test based on ranked QoL scores. If the questionnaire developers provide guidelines for scoring in the presence of missing data, we will

follow those guidelines. Alternatively, we will tally the number of questionnaires for which a particular data item is missing.

- Correlation between isoquercetin dose, plasma PDI inhibitory activity, and reduction in D-dimer or VTE incidence
- Cumulative incidence of VTE according to Khorana score³⁷
- At completion of phase II portion, we will compare the cumulative incidence of VTE of all 60 patients enrolled with similar historical population. As described above the overall cumulative incidence of VTE with similar inclusion criteria and design was 11%. We hypothesize the cumulative incidence of VTE in the phase II cohort will be 4%. Based on these assumptions, the power for this comparison is 80% (N=60 with a 1-sided alpha of 0.1 comparing 4% to historical 11% cumulative incidence rate using a Fisher exact test.)

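### The regressions for chemotherapy and growth factors on VTE and TFMP omit cancer diagnosis, so these terms may partly measure cancer type

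*Combined protocol and SAP*

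**What the plan says.** Section 1.3 sets the objective: "To investigate the influence of chemotherapy, blood counts, growth factors, ECOG performance status on tissue factor bearing microparticle levels as well as VTE risk". Section 14.2 gives one model per outcome.

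- VTE: "Fine and Graey regression modelling will be performed to assess the influence of chemotherapy, blood counts, growth factors, ECOG performance status on VTE risk".
- TFMP: "Linear regression modelling will be performed to assess the influence of chemotherapy, blood counts, growth factors, ECOG performance status on TFMP levels".

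Neither sentence mentions cancer diagnosis, and neither says what chemotherapy contrasts. Section 3.1 requires every patient to meet "Receiving or scheduled to receive first or second line chemotherapy", so the variable cannot be chemotherapy against none. It could be regimen, line, or already started against scheduled.

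Elsewhere the protocol treats cancer type as important:

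- Section 2.2: "There is a 10-fold greater rate of VTE among patients suffering from ovarian, brain, and pancreatic cancers compared to those with other histologies". The same section says that the microparticles linked to VTE appear to come from the tumor.
- Section 14.1.2.4: the incidence of thrombosis "varies between 2-40% based on histology, stage, chemotherapeutics, additional risk factors and mode of surveillance".
- Section 14.1.2.2: randomisation is stratified by cancer diagnosis.
- Section 14.2, a separate item: "Correlation between complete blood count, d-dimer, ECOG, histology, stage, and TFMP levels will be determined by assessing the correlation coefficient".

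**The concern.** The trial pools three cancers (section 3.1.1). A variable that drives the outcome and also differs between exposure groups confounds an exposure coefficient when it is left out. The protocol supplies the first half of that condition for cancer type: histology drives VTE, and a tumor origin makes a link with TFMP plausible. The second half, that regimen or growth-factor use differs by cancer, is plausible but not documented.

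If it does differ, a regimen used mainly in the highest-risk cancer would appear to raise VTE risk, and possibly TFMP, even if it did neither. The objective asks about influence, so a reader would take the coefficient as an effect of the regimen. The other uses of cancer type do not repair this. Stratified randomisation balances the arms, not the regimens. A correlation of histology with TFMP adjusts no regression coefficient. The Khorana analysis is separate, and the score as described in section 2.2 has no cancer-site component.

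**Working it through.** The documents give no power or effect size for these two models, so there is no planned figure to reproduce. The check asks what the unadjusted VTE model would show for a regimen with no effect.

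**Inputs from the documents.** VTE of 11% on placebo and 4% on isoquercetin, and 618 patients (14.1.2.4). The mean rate is (11% + 4%)/2 = 7.5%.

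**Assumptions, not in the documents.** One third of patients have pancreatic cancer. Their VTE risk is R times that of the other two cancers, with R from 2 to 10. The regimen goes to 80% of pancreatic and 10% of other patients, or to 60% and 20%.

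**Worked case, R = 10, use 80%/10%.**

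- Risk in the other cancers = 0.075/(10 × 1/3 + 2/3) = 1.875%; pancreatic risk = 18.75%.
- Users: 0.80 × 1/3 = 0.267 pancreatic and 0.10 × 2/3 = 0.067 other, so 80% of users are pancreatic.
- Non-users: 0.067 pancreatic and 0.600 other, so 10% are pancreatic.
- VTE in users = 0.8 × 18.75% + 0.2 × 1.875% = 15.4%. VTE in non-users = 0.1 × 18.75% + 0.9 × 1.875% = 3.6%.
- Crude ratio = 4.3, where the true ratio is 1.

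**General form.** The 7.5% cancels. The ratio is (0.8R + 0.2)/(0.1R + 0.9) for 80%/10% use. For 60%/20% use, 60% of users and 20% of non-users are pancreatic, and the ratio is (0.6R + 0.4)/(0.2R + 0.8).

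| R | 80%/10% use | 60%/20% use | equal use |
|---|---|---|---|
| 2 | 1.8/1.1 = 1.6 | 1.6/1.2 = 1.3 | 1.0 |
| 3 | 2.6/1.2 = 2.2 | 2.2/1.4 = 1.6 | 1.0 |
| 5 | 4.2/1.4 = 3.0 | 3.4/1.8 = 1.9 | 1.0 |
| 10 | 8.2/1.9 = 4.3 | 6.4/2.8 = 2.3 | 1.0 |

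**Would it look significant?** With 618 patients split evenly, expected events are 309 × 0.11 + 309 × 0.04 = 46. One third of patients are users in both patterns, so z is about ln(ratio) × √(46 × 1/3 × 2/3) = ln(ratio) × 3.20. For a ratio of 3.0, z = 3.51, and the chance of exceeding 1.96 is Φ(3.51 − 1.96) = 94%. For 1.64 (the 1.8/1.1 entry), z = 1.57 and the chance is 35%. For 1.33 (the 1.6/1.2 entry), z = 0.92 and the chance is 15%. The nominal rate is 5%. This treats a single crude exposure with no other terms.

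**Does adjustment cure it?** A simulation used 618 patients, an inert regimen, VTE as a binary day-56 outcome (a simplification of the Fine-Gray model), a two-sided 5% test and 4,000 runs per scenario. With one third pancreatic, the unadjusted false-positive rate at R = 2 was 11% (60%/30% use) and 31% (80%/20% use). At R = 10 it was 59% and 99%. Stratified by cancer type, it was 4% to 6% in every scenario.

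**TFMP model.** The documents give no TFMP levels by cancer type. If mean TFMP differs by D between pancreatic and other patients, an inert regimen entered alone would show a difference of (0.8 − 0.1)D = 0.7D at 80%/10% use, or (0.6 − 0.2)D = 0.4D at 60%/20%.

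**Price of adjusting.** At 80%/10%, the correlation of regimen with pancreatic cancer is (0.267 − 1/9)/(2/9) = 0.70, so standard errors grow by 1/√(1 − 0.49) = 1.40. At 60%/20%, it is (0.200 − 1/9)/(2/9) = 0.40, and the factor is 1/√(1 − 0.16) = 1.09.

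**The case against.** The strongest reply is that the two sentences in 14.2 name exposures of interest, not a closed covariate list. They do not say whether the models are univariable or multivariable, and an analyst could add diagnosis without any design change. This stands as a reading of the text: the documents do not show a decision to exclude cancer type. But then no adjustment set is specified, and the same sentence is needed.

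The second reply also stands: the size rests on assumptions. The documents contain no regimen or growth-factor distribution, and with equal use across cancers the bias is zero. A reader might take it as given that regimen follows diagnosis, but no section says so.

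A reader might also infer that the protocol puts pancreatic VTE risk at ten times that of the other cancers enrolled. It does not. The 10-fold figure in 2.2 pools ovarian, brain and pancreatic cancers against all other histologies. No ratio against lung and colorectal cancer is given, so 10-fold serves here only as the upper end of a range.

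Finally, these are secondary models with no alpha, power or decision attached. That limits the consequence but does not remove the bias.

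**Conclusion.** The point holds as a conditional one. The two models omit a factor that the protocol itself identifies as a driver of VTE, and nothing else in the plan adjusts for it. If regimen or growth-factor use differs by cancer, the coefficients for these terms will partly reflect cancer type. For an inert regimen and one third pancreatic patients, the false VTE ratio is 1.6 to 4.3 under a strong link (80% versus 10%), 1.3 to 2.3 under a weaker one (60% versus 20%), and 1.0 with equal use. No comparable figure can be given for growth factors, or in absolute units for TFMP, because the documents hold no data to base one on.

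Two wider readings are not supported. The absence of randomised arm from the models is not a source of confounding for baseline factors, since phase III allocation is random and stratified by diagnosis. And the primary randomised comparison of VTE is not affected; the scope is these secondary analyses only.

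**What to change.** In section 14.2, amend the two regression items along these lines:

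> The linear TFMP model and the Fine-Gray VTE model will be stratified by, or adjusted for, cancer diagnosis (pancreatic, colorectal, non-small cell lung). The chemotherapy variable will contrast [regimen, line, or started versus scheduled, to be stated]. Chemotherapy and growth-factor terms will be reported from the adjusted models. Where a regimen is used in one cancer only, its effect will be reported as not estimable.

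For the VTE model, stratification is attractive: it spends no coefficients on diagnosis, where covariate adjustment for three cancers takes two, and only about 46 events are expected. For the same reason the number of other terms should be kept small. Stage and randomised arm may be added for precision but are optional.

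The cost is a few sentences and no new data, because diagnosis is already a randomisation factor. The statistical price is wider intervals for the chemotherapy terms: about 9% wider under the weaker link and up to about 40% if regimen tracks diagnosis closely.

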2 BACKGROUND

2.1 Study Agent(s) - Isoquercetin

Isoquercetin is naturally occurring flavonol present in a number of fruits and vegetables such as berries, apples, and onions. Isoquercetin is the 3-0 glucoside form of the flavonol quercetin which is designated as GRAS (generally recognized as safe) by the Food and Drug Administration.¹ Recent studies have demonstrated potent antithrombotic activities of quercetin and related flavonoids in vitro and in animal models through inhibition of extracellular protein disulfide isomerase (PDI).² The goal of this trial is to evaluate the anticoagulant and antithrombotic activity of isoquercetin in patients with advanced malignancy.

Mechanism of action:

Extracellular disulfide isomerization has been explored as a regulatory pathway in platelet activation and fibrin generation. Protein disulfide isomerase is a thiol isomerase that is secreted by platelets and endothelial cells following activation and localizes to the membrane surface.³⁻⁵ The hemostatic targets of extracellular PDI continue to be elucidated and may include tissue factor and platelet integrins such as $\alpha II\beta IIIa$. The Furie laboratory recently demonstrated the critical role of extracellular PDI in regulating platelet thrombus formation and fibrin deposition in vivo.⁶ Employing intravital fluorescence microscopy to monitor a laser-induced vascular injury in mice, it was observed that inhibition of PDI with either bacitracin, a non-specific thiol isomerase inhibitor, or a specific and inhibitory monoclonal anti-PDI antibody completely blocked both platelet thrombus formation and fibrin generation in vivo.

Following the observation that inhibitory antibodies against PDI block platelet thrombus and fibrin generation in vivo, a high throughput screen identified several related flavonoids (quercetin-3-rutinoside and isoquercetin) as potent inhibitors of PDI.² The Kd of quercetin-3-rutinoside for PDI in vitro is 2.8 μ M as determined by surface plasmon resonance (SPR). PDI inhibition appears to be specific without evidence of significant inhibition of other thiol isomerases such as ERp57, ERp5, ERp72, or thioredoxin.

We recently conducted a pharmacokinetic/pharmacodynamic study to assess the PDIinhibitory activity of isoquercetin in humans. Following an oral dose of isoquercetin (1000 mg capsules), the median peak concentration was 4.45 μ M with a half-life of 8.2 hours. PDI inhibitory activity of plasma was measured using the fluorescent substrate dieosin glutathione disulfide (di-E-GSSG) to liberate a self-quenching N-terminal GSSG residue following cleavage of a disulfide bond.⁷⁻⁹ In all study subjects, we detected significant PDI-inhibitory activity in plasma following the oral administration of isoquercetin 1000 mg capsule.¹⁰

Quercetin as an antithrombotic agent

The antithrombotic potential of flavonoids first garnered attention in the 1990's following the publication of several large epidemiologic studies. In the Zupthen Elderly Study, the group of individuals who consumed over 30 mg of flavonoids daily experienced a nearly 70% reduction in mortality from myocardial infarction (adjusted RR 0.32, 95% CI 0.15-0.71) compared with those individuals who consumed less than 20 mg daily.¹¹ A prospective study of nearly 35,000 postmenopausal women demonstrated that flavonoid consumption reduced both cardiovascular and overall mortality¹² which was also confirmed in a meta-analysis of 7 cohort studies.¹³ Flavonoid consumption has also been linked with a decreased incidence of nonfatal and fatal stroke.^{14,15} Attempts have been made to identify which thrombotic risk factors are modulated with dietary flavonoid consumption but endpoints such as blood pressure, high and lowdensity lipoprotein concentrations, and flow-mediated dilatation have yielded inconsistent results. Flavonoids such as isoquercetin are known to inhibit platelet function in vitro.¹⁶⁻¹⁹ The ingestion of either onion soup or quercetin -4'-O-β-D-glucoside (the predominant quercetin found in onions) inhibited ex vivo platelet aggregation.^{20,21} However there has never been a late stage clinical study on the use of isoquercetin to specifically prevent thrombotic events in humans.

CONFIDENTIAL This document is confidential. Do not disclose or use except as authorized.

Selection of dose:

The inhibitory IC50 of PDI activity in vitro for isoquercetin metabolites ranges between 3-10uM.² Following the oral administration of isoquercetin (1000 mg) in healthy volunteers, the peak concentration of isoquercetin metabolites in healthy volunteers was 4.45μ M and was associated with 67% inhibition of PDI activity in plasma at 4 hours.¹⁰ Isoquercetin is widely available as a health food supplement and small clinical studies have not demonstrated toxicity. In a pilot trial conducted in 16 patients with mild cognitive impairment, isoquercetin 350 mg and ascorbic acid 400 mg taken for 6 months demonstrated a positive trend in cognitive function without any reported side effects (Investigators Brochure). In another study designed to evaluate the effect of isoquercetin and quercetin 1000 mg daily for two weeks without toxicity.²² Based on in vitro, animal, and human data as well as safety profile of isoquercetin (and parent compound quercetin), the planned sequential dosing cohorts for the clinical phase II trial are 500mg and1000 mg once daily.

Absorption, Metabolism, and Bioavailability

A number of clinical studies have investigated the metabolic fate of quercetin and its glucosides. Isoquercetin is better absorbed than quercetin aglycone, possibly due to increased stability at low pH.²³ The pharmacokinetic study we conducted in healthy adults (isoquercetin 1000 mg capsules) AUC was 1714 and T ½ of 8.23 hours. Isoquercetin undergoes deglycosylation by an extracellular β -glycosidase on the brush border of enterocytes yielding the aglycone.^{24,25} Although the absorption of quercetin and quercetin glucosides differ, all forms of quercetin are metabolized both in the enterocyte and liver and circulate as similar glucuronated, sulfated, and methylated conjugates.²⁶⁻²⁸ These conjugates have demonstrated biologic activity ^{2,29,30}.

Distribution

Isoquercetin and its metabolites possess high affinity for serum albumin.³¹ Quercetin metabolites did not accumulate in tissue following four weeks of daily administration to pigs. Only the organs involved in metabolism and excretion such as the small intestine, liver, and kidney, contained higher concentrations than plasma³². The elimination of absorbed quercetin follows a biphasic profile, likely due to enterohepatic recirculation following elimination of quercetin metabolites in bile.^{31,33}

Excretion

Following metabolism in the liver and/or degradation in the intestine, quercetin is excreted as exhaled CO_2 with smaller amounts found in feces and urine.^{25,34}

